- 18. The defined wider visit window can be applied, if patients are not able to strictly follow the pre-specified visit schedules, due to a prolonged public holiday.

Study Visit	Rand. Visit	Visit 6	Visit 7	Visit 8	Visit 9	Visit 10	Visit 11	Visit 12	Visit 13	Visit 14	EOS 9
28-day randomized treatment study phase Day ⁷	Day 1 ¹²	Day 2 ¹²	Day 5 ¹²	Day 8 ¹²	Day 12 ¹²	Day 15 ¹²	Day 19 ¹²	Day 22 ¹²	Day 26 ¹²	Day 29 ¹²	Day 35 ¹²
Accepted visit window during prolonged public holidays ⁸			Day 3-6	Day 7-9	Day 10-13	Day 14-17	Day 18-20	Day 21-24	Day 25-27	Day 28-31	Day 32-43
Eligibility criteria	Х										
Physical exam including weight ^{3, 13}	Х					Х				Х	Х
Access IVRS/IWRS ¹⁰	Х			Х		Х		Х			
Study drug (IP) dispensation ¹¹	Х			Х		Х		Х			
Study drug (IP) administration ⁴	Х	Х	Х	Х	Х	Х	Х	Х	Х		
ECG ³	Х			Х		Х		Х		Х	Х
Vital signs ³	Х					Х				Х	Х
Concomitant medications	Х	Х	Х	Х	Х	Х	Х	Х	Х	Х	Х
Adverse events (including SAEs)	Х	Х	Х	Х	Х	Х	Х	Х	Х	Х	Х
Potassium ⁶	X^2	Х	Х	Х	Х	X^2	Х	Х	Х	X^2	X^2
Clinical chemistry ^{1,3}	Х					Х				Х	Х
Hematology ^{1,3}	Х					Х				Х	Х
Urinalysis 1,3	Х					Х				Х	Х
Urine HCG											X^5
IP Reconciliation										Х	

Table 2Study Plan detailing the procedures: 28-day randomized treatment study phase

1. Parameters to be measured are detailed in Table 3.

2. Potassium will be measured fasting prior to the 1st daily dose as part of the clinical chemistry panel on Day 1, 15, 29, 35 in the 28-day randomized treatment study phase.

3. Physical Exam, ECG, Vital signs, weight, urinalysis, clinical chemistry including S-Aldo and P-Renin, and hematology parameters will be measured fasting (nothing by mouth except water for a minimum of 8 hours prior to potassium sample collection at the clinic); On the 28-day randomized treatment study phase Days 1,15, 29, and 35(EOS), blood sample which including S-Aldo and P-Renin test need to be collected prior to 10am after the patient has been upright for at least 2 hours and before the ECG.

4. Study drug will be administrated in the clinic on Day 1,2,5,8,12,15,19,22 and 26. If a patient develops i-STAT potassium values between 3.0 mmol/L and 3.4 mmol/L, inclusive (confirmed by taking a second potassium

measurement after a 10 ± 2 -minute interval, and both i-STAT values meet the study drug adjustment rule), dosing will be reduced from qd to every other day for the remainder of the study.

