- 5. For women of Childbearing potential, using-HCG will be measured at clinic, using the tube provided by Central Laboratory.
- 6. All potassium samples are analyzed by i-STAT and by the Central Laboratory on all occasion. And haemolysed samples should not be sent to the Central Lab for potassium, the sample should be re-drawn to obtain a sample showing no haemolysis. For diabetic patients all blood potassium samples should be collected prior to insulin administration whenever possible.
- 7. If a scheduled clinic visit falls on a weekend or short public holiday during the 28-day randomized treatment study phase, the scheduled visit may take place either 1 day early or 1 day late (i.e., within±24 hours of the scheduled day) for the 28-day randomized treatment study phase Days 5, 8, 12, 15, 19, 22, 26 and 35, up to 2 days late for the 28-day randomized treatment study phase Day 2 or 2 days early for Day 29. If the Day 29 visit is conducted early, the patient must take IP through Day 28 per protocol.
- 8. The defined wider visit window can be applied, if patients, are not able to strictly follow the pre-specified visit schedules, due to a prolonged public holiday. If the wider visit windows are applied for a particular visit, it is important that visits before and after such a visit also follows the wider visit windows. This will only apply during prolonged public holidays. Patients are expected to follow the pre-specified visit schedule once the prolonged holiday period is over.
- 9. EOS occurs 7 ± 1 day after the last administration of IP.
- 10. Access IVRS/IWRS on visit indicated or if patient permanently discontinues dosing before the end of the 28day randomized treatment study phase.
- 11. Due to a public holiday, patients may visit the clinic up to two days after the pre-specified visit schedules, the site investigator can access the IVRS/IWRS in an earlier visit; and the system will assign the patient a new 28-day randomized treatment study phase IP kit containing an additional 7-day supply of IP.
- 12. Study Day in Table 2 is for the 28-day randomized treatment study phase.
- 13. Targeted physical examination will be conducted on Days 1, 15, 29, and Day 35 (EOS) during the 28-day randomized treatment study phase, please refer to Section 5.2.2.

4.1 **Optional Pre-screening period (Visit 1)**

The Pre-screening visit is optional. Study procedures will be performed according to the Study Plan in Table 1.

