If a patient develops i-STAT potassium values between 3.0 mmol/L and 3.4 mmol/L, inclusive (confirmed by taking a second potassium measurement after a 10 ± 2 minute interval), during the 28-day randomized treatment study phase, dosing will be reduced from qd to qod for the remainder of the study.

Patients with confirmed potassium <3.0 mmol/L in both study phases should discontinue from therapy as per Section 3.9.

Patients with confirmed i-STAT potassium >6.2 mmol/L during the 28-day randomized treatment study phase should discontinue from therapy as per Section 3.9.

For doses administered in the clinic during both study phases each dose will be individually dispensed by designated, trained site staff.

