3.3.1.2 Definition of On-Treatment

For OLP: Any measurements that have an onset day on or after the date of first dose of openlabel study treatment and no later than the date of last dose of open-label study treatment + 1 day.

For RTP: Any measurements with an onset date more than one day after the day of last dose of open label study medication, and either on or after the day of first dose of randomized study medication, and no later than the day of last dose of study medication +1 day.

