4.3.1 Exposure

4.3.1.1 Definitions and Derivations

Duration of exposure is defined as the number of days between the first and the last dose of IP + 1 day, for each treatment period. Duration of exposure for subjects on every other day dosing is defined as the number of days between the first and the last dose of IP where subjects have a planned dose of IP + 2 days.

Actual Exposure

Actual exposure for each subject will be obtained by summing up the days for which at least one dose of the drug was taken, excluding dose interruptions, and for each treatment arm and overall.

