4.3.3.2 Presentations

Descriptive statistics by time of assessment will be presented for each laboratory parameter including other serum electrolytes separately for OLP and RTP. All laboratory values will be classified as low, normal, or high based on normal ranges supplied by the central laboratory. For purposes of analyses, laboratory results based upon standardized units will be used.

For each summary of continuous variables, the number of non-missing observations, mean, median, standard deviation, minimum, and maximum values will be presented by study phase and treatment group for OLP and RTP.

Absolute values and change from baseline for all continuous haematology and clinical chemistry parameters will be summarized for OLP and RTP by treatment arm and scheduled visit.

Box plots of absolute values by scheduled visit, and box plots of change from baseline by visit, may be presented for certain parameters if warranted after data review.

Any treatment-emergent laboratory data reported as abnormal according to reference values as well as individuals with treatment-emergent, abnormal serum laboratory values will be summarized and listed for the relevant safety analysis set by treatment group presented separately for the OLP and the RTP.

Additionally, subject listings and summary of all on-treatment hematology and chemistry changes will be provided for OLP and RTP by treatment group.

Elevated liver test results

Maximum on-treatment ALT and AST versus maximum total bilirubin will be presented. Listings of liver biochemistry test results will be provided, separately for OLP and RTP.

Hypokalemia

Tabulation of the number and percentage of subjects with hypokalemia (<2.5 mmol/L, <3 mmol/L, <3.5 mmol/L) at any point during a phase (OLP and RTP), while on treatment, will be presented by treatment group.

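### The +1 day on-treatment cut-off keeps the Day 29 visit for daily dosing but drops it for every-other-day patients last dosed on Day 27

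*SAP*

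**What the plan says.** - **On-treatment window.** SAP 3.3.1.2 counts a randomized-phase measurement as on treatment if it falls "no later than the day of last dose of study medication +1 day". There is no separate rule for every-other-day dosing.
- **Switch rule.** Under Protocol 7.2, after a confirmed i-STAT value of 3.0-3.4 mmol/L in the randomized phase, "dosing will be reduced from qd to qod for the remainder of the study".
- **End of dosing.** The notes to Protocol Table 2 say of an early final visit that "the patient must take IP through Day 28 per protocol". They also say "Study drug will be administrated in the clinic on Day 1,2,5,8,12,15,19,22 and 26", so no clinic dose is listed for Day 29. The follow-up visit is placed at Day 35, and "EOS occurs 7 ± 1 day after the last administration of IP".
- **Hypokalaemia table.** SAP 4.3.3.2 tabulates subjects below 2.5, 3.0 and 3.5 mmol/L "at any point during a phase (OLP and RTP), while on treatment, will be presented by treatment group".
- **Exposure.** SAP 4.3.1.1 gives every-other-day patients their own duration rule, counting the days between first and last dose "where subjects have a planned dose of IP + 2 days". Other patients get +1 day.
- **Last-dose footnotes.** Footnote iii to SAP Table 3 and footnote 3 to Protocol Table 6 both identify Day 29 with the day of last dose.

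**The concern.** The +1 day allowance works for daily dosing because the Day 29 visit comes one day after the planned last dose. On every-other-day dosing the planned last dose can be Day 27, with nothing due on Day 28. That patient has followed the schedule and attends Day 29 at the end of a dosing interval, just as a daily patient does, yet the visit is classed as off treatment.

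The patients concerned were moved to the reduced schedule because their potassium was low. Hypokalaemia is one of the two risks named in Protocol 1.3.3, and the SAP defines it from laboratory values rather than coded terms. Removing values from an any-time count can only lower it.

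The same window governs treatment-emergent laboratory and vital-sign abnormalities, maximum on-treatment liver tests, QTcF categories, the last on-treatment ECG classification and on-treatment adverse events. Between randomization and follow-up, the full chemistry, haematology and vital-sign assessments are scheduled only on Days 15 and 29. For a patient switched after Day 15, Day 29 is the only such assessment on the reduced schedule before follow-up.

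**Working it through.** **Schedule check.** Last planned dose Day 28 + 7 = Day 35, which reproduces the follow-up day in Protocol Table 2. Day 28 is therefore taken as the last possible dosing day.

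**Window end = last dose day + 1.**
- Daily dosing: 28 + 1 = 29. Day 29 is inside.
- Every other day, last dose Day 28: 28 + 1 = 29. Inside.
- Every other day, last dose Day 27: 27 + 1 = 28. Day 29 is outside.

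**How often the last dose is Day 27.** A switch can be triggered at the dosing visits on Days 2, 5, 8, 12, 15, 19, 22 and 26. The documents do not say on which day the new schedule starts, so both options were run forward to Day 28:

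| Start of every-other-day dosing | Switch visits ending on Day 27 | Share |
|---|---|---|
| Dose taken on the visit day | Days 5, 15, 19 | 3/8 = 37.5% |
| Visit day skipped, dose next day | Days 2, 8, 12, 22, 26 | 5/8 = 62.5% |

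These shares weight the visits equally. If switches were spread evenly over Days 2-26 (25 days), the shares would be 12/25 = 48% and 13/25 = 52%.

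**Comparison with the exposure rule.** SAP 4.3.1.1 defines a duration. Taking the days between two doses as their difference, and a first dose on Day 1:

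| Schedule, last dose | Duration | Exposure ends | On-treatment ends | Margin |
|---|---|---|---|---|
| Daily, Day 28 | 27 + 1 = 28 days | Day 28 | Day 29 | 1 day |
| Every other day, Day 27 | 26 + 2 = 28 days | Day 28 | Day 28 | 0 days |
| Every other day, Day 28 | 27 + 2 = 29 days | Day 29 | Day 29 | 0 days |

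With last dose + 2 for every-other-day patients, the window ends on Day 29 or Day 30. The margin becomes 1 day in both rows, and none of the 8 switch visits loses a Day 29 sample under either starting rule.

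**Number of samples (assumption).** The documents give no switch rate. Two hypokalaemia figures serve for scale:
- Protocol 1.3.2, 4.1% of ZS patients, applied to 200 active patients: 0.041 × 200 = 8.2 switched; × 3/8 = 3.1, × 5/8 = 5.1.
- Protocol Figure 2, 9.8 for 10 g, read as a percentage-point excess and applied to 100 patients: 9.8 switched; × 3/8 = 3.7, × 5/8 = 6.1. The figure's interval of 1.6 to 18 gives from 1.6 × 3/8 = 0.6 to 18 × 5/8 = 11.3.

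**Visits off the nominal day.** The final visit may be held up to "2 days early for Day 29", and a visit on Day 27 or 28 stays inside the window. A holiday-window visit on Day 30 or 31 is outside it even for a daily patient last dosed on Day 28.

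**The case against.** A reader might infer that SAP 3.3.1.2 and 4.3.1.1 contradict each other, with the patient on treatment at Day 29 under one and off under the other. They do not. The +2 days in 4.3.1.1 is part of an inclusive count, so a last dose on Day 27 gives exposure through Day 28, the same day on which 3.3.1.2 closes. The exposure rule shows only that the SAP treats an every-other-day dose as covering two days. The case therefore rests on unequal margins, and that part stands.

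The data are also not lost from the report. Laboratory values, vital signs and ECG are summarized by visit, and individual values are listed. The overall adverse event table is repeated for all events in the randomized phase, and Day 29 potassium stays in the treatment-policy efficacy analyses.

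The effect on the hypokalaemia table is narrow. Switched patients already had a confirmed value below 3.5 mmol/L, so that row should barely move. A missed count in the lower rows needs a first value below 3.0 mmol/L on Day 29 itself, after dosing was reduced, and the documents give no rate for this. However, a confirmed i-STAT value below 3.0 leads to discontinuation. A patient still dosing on Day 27 would normally have had none, so a Day 29 value that low would usually be a new event.

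On the Table 3 and Table 6 footnotes, with a last dosing day of Day 29, nothing is excluded. That reading does not fit the Table 2 notes, the four 7-day kits or follow-up at Day 35.

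**Conclusion.** The point holds as a cheap improvement. The uniform +1 day cut-off gives daily patients one day beyond their exposure period and every-other-day patients none. It classes a Day 29 visit as off treatment for about 38-63% of switched patients who attend on that day. The range assumes dosing through Day 28 and equal weight per switch visit.

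In absolute terms this is perhaps 3 to 6 Day 29 samples. That count borrows hypokalaemia rates from earlier studies: neither is a switch rate, and 9.8 is a difference from placebo with a wide interval. It counts samples, not missed hypokalaemia cases, whose number cannot be estimated from the documents.

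Two further inferences go too far. The documents give no placebo hypokalaemia rate, so they do not show that nearly all affected patients would be on ZS. Nor do they support a material understatement of hypokalaemia overall. The exposure is confined to on-treatment tabulations, mainly the rows below 3.0 and 2.5 mmol/L, and the primary analysis is untouched.

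**What to change.** In SAP 3.3.1.2, end the randomized-phase on-treatment window at last dose +2 days for patients who are on every-other-day dosing at their last dose, and keep +1 day for the others. Both schedules then have the same one-day margin beyond the exposure period in 4.3.1.1.

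Reconcile footnote iii of SAP Table 3 and footnote 3 of Protocol Table 6, which place the last dose on Day 29, with the Protocol Table 2 notes on dosing through Day 28.

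The cost is one SAP clause and one derivation flag from existing dosing records. The downside is an on-treatment window one day longer for these patients: one last dosed on Day 28 would be covered to Day 30. The change is to analysis definitions only and implies no change to dosing.

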3.3.1.3 Definition of Treatment-emergent

For OLP: Any measurements reported as 'abnormal' whilst on-treatment (defined as per Section 3.3.1.2),but were previously reported as 'normal' at OLP Baseline (defined as per Section 3.3.1.1)

For RTP: Any measurements reported as 'abnormal' whilst on-treatment (defined as per Section 3.3.1.2), but were previously reported as 'normal' at RTP Baseline (defined as per Section 3.3.1.1)

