1. INTRODUCTION

1.1 Background and rationale for conducting this study

Potassium is a ubiquitous ion, involved in numerous processes in the human body. It is the most abundant intracellular cation and is critically important for numerous physiological processes, including maintenance of cellular membrane potential, homeostasis of cell volume, and transmission of action potentials. The main dietary sources are vegetables (tomatoes and potatoes), fruit (oranges, bananas) and meat. The normal potassium values in serum (S-K) are between 3.5 and 5.0 mmol/L, with the kidney being the main regulator of potassium values. The renal elimination of potassium is passive (through the glomeruli) with active reabsorption in the proximal tubule and the ascending limb of the loop of Henle. There is active excretion of potassium in the distal tubules and the collecting duct, both of which processes are controlled by aldosterone.

Hyperkalemia develops when there is excessive production (oral intake, tissue breakdown) or insufficient elimination of potassium. Insufficient elimination, which is the most common cause of hyperkalemia, can be hormonal (as in aldosterone deficiency), pharmacologic (treatment with angiotensin-converting-enzyme [ACE] inhibitors or angiotensin-receptor blockers [ARBs]) or, most commonly, due to reduced kidney function. Increased extracellular potassium values result in depolarization of the membrane potential of cells. This depolarization opens some voltage-gated sodium channels, but not enough to generate an action potential. After a short period of time, the open sodium channels inactivate and become refractory, increasing the threshold to generate an action potential. This leads to impairment of the neuromuscular, cardiac, and gastrointestinal organ systems, and is responsible for the symptoms seen with hyperkalemia. Of

greatest concern is the effect on the cardiac system, where impairment of cardiac conduction can lead to fatal cardiac arrhythmias such as asystole or ventricular fibrillation. Because of the potential for fatal cardiac arrhythmias, hyperkalemia represents an acute metabolic emergency that must be immediately corrected.

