3.3 General Considerations

All efficacy analyses will be performed separately for the open-label initial phase and the 28day randomized treatment study phase using their respective full analysis sets. Safety data will be separately summarized in a descriptive manner on the safety analysis sets for the OLP and the RTP, respectively.

All efficacy data will be listed by subject and will include S-K assessments data and efficacy response (achieve normokalemia) data. Study population listings will include disposition, protocol deviations, subjects excluded from efficacy analysis, demographic and baseline characteristics, and safety listings will include treatment compliance, adverse events, individual laboratory measurements, vital signs, physical examinations, and electrocardiograms (ECG).

Unless otherwise stated, percentages will be calculated out of the population total and for each treatment group and will be rounded to 1 decimal place. For continuous data, the mean and median will be rounded to one additional place compared to the original data, the standard deviation (SD) and standard error (SE) will be rounded to 2 additional places, and the minimum and maximum will be displayed to the same accuracy as the original data. If the number of decimal places of the original data is > 3, then the minimum and maximum will be assigned 3 decimal places, the mean and median 4 decimal places, and the SD and SE 5 decimal places.

Results of all statistical analyses will be presented using a 95% confidence interval (CI) and two-sided p-value, unless otherwise stated. All p-values will be presented to 3 decimal places. All p-values less than 0.001 will be presented as '< 0.001' and p-values greater than 0.999 will be presented as '> 0.999'.

SAS® version 9.4 or higher will be used for all analyses.

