3.3.1 General Study Level Definitions

3.3.1.1 Definition of Baseline Efficacy Baseline

For the OLP: The baseline Serum Potassium (S-K) will be established on the OLP Study Visit 3 (pre-dose) by taking the mean of 2 different S-K values.

For the RTP: The baseline S-K, S-Aldo and P-Renin will be established based on the last prerandomization measurement for S-K, S-Aldo and P-Renin, respectively, obtained during the OLP.

If baseline S-K C-lab values are missing, the i-STAT data will be used to replace them as described in Section 4.2.1.3. Subjects with missing values at baseline will be excluded from the relevant efficacy analysis.

Safety Baseline

Safety analyses will be performed separately for OLP and RTP. For change from baseline tabulations (laboratory measurements, vital signs, ECG and weight) the baseline will be defined as follows:

For OLP: Baseline will be the last non-missing measurement taken prior to first IP administration during OLP. If a measurement was taken on the date of first IP administration and no time is recorded, it is assumed that the measurement was taken pre-dose and will be considered a candidate for baseline.

For RTP: Same as OLP baseline, i.e. the last non-missing measurement taken prior to first IP administration during OLP.

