4.3.6.2 Presentations

Summary statistics for vital signs will be calculated for absolute values and change from baseline to each subsequent planned visit where applicable. For each summary, the number of non-missing observations, mean, median, standard deviation, minimum, and maximum will be presented by treatment group for each study phase (OLP and RTP).

Baseline versus maximum value on treatment shift table will be provided for all vital sign parameters.

Any treatment-emergent, abnormal vital signs will be summarized and listed for the safety analysis set by treatment group for each study phase (OLP and RTP).

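### The treatment-emergent laboratory flag requires a normal baseline, so high-to-low and low-to-high changes cannot be counted as treatment-emergent

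*SAP*

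**What the plan says.** SAP 3.3.1.3 sets one rule per phase. In the OLP, a measurement is treatment-emergent if it is abnormal on treatment "but were previously reported as 'normal' at OLP Baseline (defined as per Section 3.3.1.1"). In the RTP, the condition is the same with the other baseline: "but were previously reported as 'normal' at RTP Baseline (defined as per Section 3.3.1.1").

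SAP 4.3.3.2 uses three classes: "All laboratory values will be classified as low, normal, or high based on normal ranges supplied by the central laboratory". The flag then selects what is tabulated: "Any treatment-emergent laboratory data reported as abnormal according to reference values" is to be summarised and listed by treatment group, separately for each phase. On denominators, SAP 3.3 says that, unless stated otherwise, "percentages will be calculated out of the population total and for each treatment group"; 4.3.3.2 states nothing different.

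SAP 3.3.1.1 gives two RTP baselines. The efficacy baseline for S-K, S-Aldo and P-Renin is the last value before randomisation. The safety baseline reads: "For RTP: Same as OLP baseline, i.e. the last non-missing measurement taken prior to first IP administration during OLP". SAP 3.3.1.3 points to 3.3.1.1 without saying which applies.

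For vital signs, SAP 4.3.6.2 says: "Any treatment-emergent, abnormal vital signs will be summarized and listed". It does not say how abnormal is decided.

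SAP 4.3.3.2 also plans outputs that do not use the flag: a hypokalaemia table (below 2.5, 3 and 3.5 mmol/L at any time on treatment), change from baseline by visit, and listings and a summary of on-treatment haematology and chemistry changes.

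**The concern.** The word abnormal pools two opposite states. A patient who starts high and becomes low has a new finding on treatment, but the flag treats it as a continuing abnormality and drops it.

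The gap falls on this trial's own population. Protocol 3.1 admits patients only with two i-STAT potassium values of at least 5.1 mmol/L, and Protocol 1.1 says: "The normal potassium values in serum (S-K) are between 3.5 and 5.0 mmol/L". Protocol 1.3.3 names hypokalaemia as a risk of ZS. Any patient whose central-laboratory S-K is classed high before open-label dosing cannot be flagged for low S-K in the OLP, nor in the RTP if the safety baseline applies.

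The other chemistry outcomes named in Protocol 2.3 (calcium, magnesium, sodium, phosphate, bicarbonate and BUN) have the same gap. They also lack a fixed cut-off table, and no blood chemistry shift table is specified.

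At stake is whether the treatment-emergent laboratory table can be read at face value, and whether it agrees with the hypokalaemia table in the same report.

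**Working it through.** The plan gives no figure to reproduce here. The check applies the written rule to every combination of baseline and on-treatment class, beside a directional rule (on-treatment class abnormal and different from the baseline class).

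| Baseline | On treatment | SAP 3.3.1.3 | Directional rule |
|---|---|---|---|
| low | low | no | no |
| low | normal | no | no |
| low | high | **no** | **yes** |
| normal | low | yes | yes |
| normal | normal | no | no |
| normal | high | yes | yes |
| high | low | **no** | **yes** |
| high | normal | no | no |
| high | high | no | no |

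The SAP rule flags 2 transitions and the directional rule flags 4. The difference is exactly high to low and low to high. Under the written rule, a patient with an abnormal baseline for a parameter can never be flagged for that parameter.

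**Size of the undercount.** For low values, let *n* and *h* be the shares of patients normal and high at baseline, and *r_n* and *r_h* their rates of becoming low on treatment. With the whole analysis set as denominator:

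- new lows among all patients = *n*·*r_n* + *h*·*r_h*
- new lows that the flag counts = *n*·*r_n*
- shortfall = *h*·*r_h*

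The documents give neither *h* (the central-laboratory limits and baseline abnormality rates are absent) nor *r_h*. The shortfall can be anything from none (nobody high at baseline) to all new lows (everybody high at baseline).

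**Illustration for S-K.** Take a patient at 5.8 mmol/L before dosing and 3.3 on treatment. If 5.8 is above the laboratory's upper limit and 3.3 below its lower limit, this patient appears in the hypokalaemia table at below 3.5 but not in the treatment-emergent table.

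**Which RTP baseline.** With the safety baseline, the reference precedes any ZS, so a high entry value blocks the flag throughout the RTP. With the efficacy baseline for S-K, the reference is the last pre-randomisation value. Randomisation requires i-STAT potassium of 3.5 to 5.0 mmol/L (Protocol 4.3.4), so few patients should be high and the RTP loss for S-K would be near zero. The OLP loss is the same kind under either reading, since both OLP baselines are taken before dosing.

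**The case against.** The strongest reply is that the example that matters most is already covered. SAP 4.3.2.1 says hypokalaemia is identified by laboratory values, and its table in 4.3.3.2 has no baseline condition. Change summaries and listings carry the remaining shifts, and SAP 3.3.3 lets summaries of extremes use all post-baseline values. Protocol 8.5.3 asks only that laboratory data be presented descriptively. All of this stands, and it limits the point to a minor one. It does not put the missing transitions back into the treatment-emergent counts, and no other clause of the SAP does so.

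A reader might infer that opposite-direction changes vanish from the report. They do not; they are absent only from the treatment-emergent summary and listing.

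A reader might also try to put a count on the loss:

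- Protocol 1.3.1 gives ZS-004 falls of 0.8, 1.2 and 1.5 mmol/L by baseline stratum. Setting their weighted mean to the 1.05 of Protocol 8.2 puts between 0.25/0.70 = 35.7% and 0.25/0.40 = 62.5% of patients at 5.5 or above.
- The 4.1% hypokalaemia rate of Protocol 1.3.2 gives 200 × 0.041 = 8.2 cases in the two ZS arms. Of these, 8.2 × 0.643 = 5.3 down to 8.2 × 0.375 = 3.1 would be flagged.

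The arithmetic is right, but the documents do not support the inference. They do not call 1.05 the ZS-004 mean fall, and they do not give the central-laboratory limits. The 4.1% is pooled over trials, while Protocol Figure 2 shows 9.8 (1.6, 18) for 10 g, with units not labelled in the text available. The calculation also needs the safety baseline to apply and low S-K to be unrelated to baseline.

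**Conclusion.** The point holds as a defect in one definition. SAP 3.3.1.3 captures two of the four moves into a new abnormal laboratory class and misses high to low and low to high, in both phases, while the patients concerned remain in the denominator. That conclusion rests only on the wording of 3.3.1.3, 4.3.3.2 and 3.3.

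S-K is the most exposed parameter in the OLP, and in the RTP if the safety baseline is meant. The other chemistry parameters share the gap and have less cover elsewhere. The number of patients affected cannot be computed from the documents.

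Severity is minor: only descriptive safety counts change, and no efficacy test or estimand uses the flag. For vital signs the same gap exists only if they too are classed low, normal or high, which the SAP does not say.

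**What to change.** In SAP 3.3.1.3, for each phase, define treatment-emergent as an on-treatment low value when the baseline was not low, or an on-treatment high value when the baseline was not high. In the same edit, state that the RTP baseline there is the Safety Baseline of 3.3.1.1. In 4.3.6.2, state whether vital signs are classed low, normal or high, and apply the same rule only if they are.

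The cost is one sentence per phase and one re-derived flag, with no new data and no extra table.

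The flag and the hypokalaemia table may still differ slightly after this change. One uses the laboratory's reference range and a baseline condition; the other uses a fixed 3.5 mmol/L and none. A footnote saying so would prevent the difference being read as an error.
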